We developed a new qualitative study to explore participants' motivations for enrolling or not enrolling in the MOVE IT study. The qualitative study consists of 1) data collection during the enrollment encounter for the purposes of conducting a discourse analysis and 2) semi-structured interviews among participants who decline MOVE IT (in-person) and enroll in MOVE IT (2 weeks after discharge from the hospital by phone). For the latter, the MOVE IT team has added additional questions pertaining to the intervention and patients' transitions from hospital to home. We engaged Penn's Mixed Methods Research Lab to support data collection, transcription, coding, and analysis; key personnel were added to the IRB application. The MOVE IT research coordinator also supported inperson data collection. The addition of this study had no impact on the RETAIN study itself, but the two were linked for regulatory/oversight purposes.

III. Final Protocol

1. Abstract

The most common and conceptually sound^{1,2} ethical concerns with incentives for research participation are that they may (1) represent undue inducements by blunting peoples' perceptions of research risks, thereby preventing fully informed consent³⁻⁵; or (2) represent unjust inducements by encouraging enrollment preferentially among the poor. Neither of these concerns has been shown to manifest in studies using hypothetical incentives for participating in hypothetical RCTs.⁶⁻⁸ But without evidence of how real incentives influence decision-making for real RCTs, practice variability remains.

We will conduct a randomized trial of 3 real incentives to participate in two parent randomized clinical trials (RCTs). Following clinicians' and research staff's preliminary determination of patients' eligibility in the parent RCT, we will assess patients' research attitudes, demographic characteristics, perceived research risks, time spent reviewing informed consent documents, ability to distinguish research from individualized patient care, and comprehension of key trial features. These quantitative assessments will be supplemented by semi-structured interviews for a selected group of participants that more deeply explore patients' motivations for participating in trials, and the relative influence of incentives on those choices.

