Given the growing gap between the supply of and demand for clinical research participants, investigators increasingly have sought to understand how people make decisions to participate in research, and specifically what investigators ethically can do to improve study enrollment.²³⁻²⁷ Among the several reasons why potential subjects would or would not participate in research, the opportunity for financial compensation or benefit often figures prominently among both patients²⁸⁻³⁰ and volunteers.^{31,32} Indeed, common sense, anecdotal experiences, and the few empirical analyses conducted to date all suggest that financial incentives can increase study enrollment, and that larger incentives are more effective than are smaller ones.^{6,7,33}

If financial incentives do indeed increase the enrollment fraction – the number of patients enrolled among all patients recruited – they could enhance considerably the scientific value and validity of the research by augmenting the precision (i.e., statistical power) of RCTs. Further, because prior studies by our team^{7,8,28} suggest that payments may influence participation decisions across socioeconomic and racial groups, it is possible that incentives could combat selective enrollment, augmenting the generalizability of RCT results. Despite these conceptual merits of incentives for research participation, and the fact that they are commonly provided, ^{34,35} the practice is controversial due to legitimate concerns regarding their unintended consequences.

There are two primary ethical concerns with providing incentives for research participation

Perhaps the most often-cited concern with paying people to participate in research is that incentives represent undue inducements – that is, they might alter peoples' perceptions of the risks associated with research participation, thereby preventing fully informed consent. ^{3-5,36-42} In the face of monetary offers, particularly those that are large and immediate, people may overlook or underestimate a study's risks, and hence consent to participate against their own better judgment. Importantly, an inducement is not undue if it merely encourages people to do things they would not do for free.^{36,37,39,42}

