All participants who are randomized and enrolled in RETAIN and consent to the BASC and MOVE IT will be debriefed on the randomization of incentives and the purpose of the RETAIN study will be explained (see Sections 8.g. and 8.h. Debriefing in BASC and MOVE IT, respectively).

d. Administration of Survey Instruments

i. BASC

Procedures for this study will commence during initial pre-screening eligibility assessment via phone for the BASC trial. During this call, all study candidates will complete an initial eligibility assessment with research staff members from the clinical site from which they are being recruited (Northwestern or Penn). Research staff will begin with the BASC eligibility screen survey, which includes basic demographic questions, as well as questions related to participants' endorsement of symptoms of clinical depression. Once a patient is determined to be preliminarily eligible for BASC, the research staff will ask the RETAIN eligibility prompt to assess for prior knowledge of the specific incentives or randomization used for RETAIN. Participants who do not have prior knowledge of the RETAIN incentives or randomization will be randomized by the research staff via the BASC trial's Data Management System (DMS) (see Section 10.a.1 Data Collection and Data Confidentiality – BASC). Prospective participants will then be introduced to BASC study basics and risks and informed that if they are determined to be eligible for the BASC study and participate in the BASC trial, they will receive \$0, \$200, or \$500 for participation.

Prospective participants who have prior knowledge of the incentives or randomization used for RETAIN will not be randomized, enrolled, or receive RETAIN-related messaging on the phone call. They will receive the standard study information regarding session and travel compensation for the BASC trial without RETAIN messaging. For information on remuneration in the BASC trial, see Section 6.d. These participants will not be debriefed or paid the RETAIN incentives.

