Before research staff finalize logistical details on the BASC study and schedule intakes for tentatively eligible patients, they will administer several RETAIN-related questionnaires to assess 1) demographics and personal financial well-being, 2) attitudes towards biomedical research, 3) prior experience in research, and 4) perceptions of research risk. The screener will administer these surveys via phone using CRF forms adopted for the RETAIN trial that will later be scanned into the BASC trial's DMS.

Participants who pass the BASC pre-screening will be scheduled to attend a 2-3½ hour Intake session for the BASC trial. During the intake session, BASC research staff at Penn and Northwestern will read a pre-BASC consent script before presenting an electronic image of the BASC informed consent/ HIPAA forms with additional information regarding the RETAIN incentive randomization condition; this electronic image will be presented via tablet or desktop. By presenting the BASC consent with randomized compensation information electronically, we will assess the amount of time participants spend reading each part of the main trial consent form. Each section (e.g., Study Introduction, Procedures by Visit, Possible Risks and Discomforts, etc.) will be presented as a survey in REDCap. Time-stamp data collected for this REDCap module will be linked by the study ID generated in the BASC Data Management System during candidates' telephone pre-screen call (see Section 10.a.1. Data Collection and Data Confidentiality - BASC).

Once participants finish reading and before signing a paper version of the BASC trial consent, they will complete brief assessments of perceptions of research risk (administered over the telephone pre-screen and again at intake – see Section 9.a. BASC Study Calendar). They will also complete assessments on perceptions of the difference between research and individualized patient care and understanding of the smoking cessation study via a trial elements quiz. All of these measures will be administered via the CRF paper and pencil processes currently used in the BASC trial. The responses to the quiz will be reviewed with participants, during which participants' questions will be answered.

ii. MOVE IT

Clinical research coordinators will identify patients through electronic health record-based screening for the MOVE IT study and preliminarily eligible patients will be approached for recruitment in their hospital rooms.

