	secondary	risk score distributions. We found that in the Ambulation trial the
	analysis of the	risk score mostly (>85%) clumped on 0, and in the smoking trial the
	risk score and	score is extremely right skewed. To better handle this sparsity of
	incentives where	data we planned a secondary analysis in which we treat the risk
	risk score is	scores as binary and compare the inferences.
	treated as a	
	binary variable (0	
	and >0).	

VI. Final Statiscal Analysis Plan

1. Background and rationale

This study is designed to provide the first-ever real-world tests of a broad range of intended and unintended consequences of financial incentives for research participation. It will do so through the conduct of two separate, but similarly designed, embedded randomized trials within actual parent clinical trials. It is our hope the findings from this study will inform research regulations and guide the use of incentives in future RCTs so as to expedite medical innovation and improve health

2. Objectives and hypotheses

The aims of this study are to (1) determine if the ethical concerns with incentives for research participation actually manifest; and (2) assess the possible scientific and ethical benefits of financial incentives for RCT participation.

We hypothesize that research incentives will:

- Augment participants' perceptions of risk without disproportionately encouraging economically disadvantaged participants to enroll
- Demonstrate an increased enrollment fraction in the parent trials, thereby enhancing the scientific value and validity of the research by augmenting the precision of the studies

3. Design and randomization

RETAIN comprises two prospective randomized controlled trials, embedded within two parent trials conducted in parallel, each comparing three intervention arms. Arms vary by the amount of the financial incentives that are offered to potential participants. Amounts offered differ on a per trial basis determined by the relative time and effort being asked of the participant for each parent trial. Assignment to arms is determined by computerized random-number generation with block randomization using variable block sizes of 3 and 6. Participants in both embedded trials have a 33.3% probability of being assigned to each RETAIN arm.

a. BASC Trial

• The Behavioral Activation and Varenicline for Smoking Cessation in Depressed Smokers Study (BASC) (NCT 02378714)

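### The undue-inducement test can show that risk sensitivity is similar across arms but cannot exclude that the offer lowers perceived risk; the one analysis that could show this is limited to consenters

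*Combined protocol and SAP*

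**What the plan says.** The final protocol's Abstract (III.1) gives the concern that incentives may "represent undue inducements by blunting peoples' perceptions of research risks, thereby preventing fully informed consent". The Background (III.2) names two routes: with a large offer, "people may overlook or underestimate a study's risks". The stopping rules (III.11.c) turn this into a test: risk perception being less strongly tied to enrolment in the higher-payment arms. Final SAP 5.c tests the interaction of incentive size and risk perception on enrolment, and excludes undue inducement if an interaction odds ratio above 2.0 can be ruled out.

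**Timing in BASC (III.8.d.i).** After randomisation, "Prospective participants will then be introduced to BASC study basics and risks and informed that if they are determined to be eligible", they will receive $0, $200 or $500. The questionnaires follow on the same call and end with "3) prior experience in research, and 4) perceptions of research risk". The scale is repeated at intake, before the consent form is signed.

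**Timing in MOVE IT (III.8.d.ii).** The amount is read out in the recruitment script. The risk scale comes later, before the consent decision. The change log records that in April 2018 the scale was added to the baseline surveys, to capture patients who decline early.

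**Expected direction.** SAP 2 hypothesises that incentives will "Augment participants' perceptions of risk without disproportionately encouraging economically disadvantaged participants to enroll".

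**Arm comparison.** SAP 6.b lists perceived risk as a secondary outcome. SAP 6.c assesses all secondary outcomes among consenters, unweighted and, where appropriate, weighted by the inverse probability of consent.

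**The concern.** Perceived risk has two jobs in this plan. It is the moderator in the primary undue-inducement test, and it is something the offer may change. A slope interaction shows whether patients act on a given level of perceived risk equally in each arm. It does not show whether the offer moved that level. A patient who sees less risk because of the money, and acts consistently on that lower perception, stays on the same slope. That is the underestimating route in the Background.

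The gap could be filled by comparing perceived risk by arm, but the plan makes that comparison only in consenters. Consent depends on perceived risk and on the incentive, so the arms being compared are no longer the randomised ones. If the money itself draws in people who see more risk, consenters in the top arm will look more risk-aware. That offsets any lowering and resembles the increase the SAP hypothesises. The trial could report undue inducement as excluded while one of its two described forms was present.

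**Working it through.** **1. The plan's own figure.** SAP 7.b states at least 80% power with 96 per cell, 50% enrolment, true odds ratio 1, margin 2.0 and one-sided 0.0427 (z = 1.72). Wald power is Φ(ln 2/SE − z).
- $0-arm odds ratio treated as known: SE = √(8/96) = 0.289; power = Φ(2.40 − 1.72) = 75.2%.
- Both arms estimated: SE = √(16/96) = 0.408; power = Φ(1.70 − 1.72) = 49.1%.

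The 80% does not reproduce this way, although the SAP expects more power from the continuous, three-level analysis. This is a separate matter and does not affect the point here.

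**2. What the interaction sees.** Let R be perceived risk without an offer, x run from 0 ($0 arm) to 1 (top arm), and P = R − δx be perceived risk after an offer that lowers it by δ. Suppose every arm acts on P with the same slope: logit Pr(enrol) = α + βP.
- Model in P (as planned): the interaction coefficient is 0 for any δ.
- Model in R (a pre-offer score): α + βR − βδx. The drop goes into the incentive main effect, and the interaction is again 0.

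**3. How often undue inducement would be excluded.** Assumptions: 576 patients, 192 in each of three ordered arms, normal scores, margin 2.0 per SD for top versus $0, one-sided 0.0427, 2,000 runs, and the middle arm shifted by half.

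| Enrolment OR per SD of risk | No drop | 0.5 SD drop | 1 SD drop |
|---|---|---|---|
| 0.50 | 88% | 87% | 88% |
| 0.67 | 93% | 93% | 94% |

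The median interaction odds ratio is 0.99–1.00 throughout. In the first row, top-arm enrolment rises from 50% to 58% and 65%. A second set-up (top versus $0, 192 each, log odds ratio −1 per SD, one-sided 0.05) gives about 80% with a 0.3–0.6 SD drop and 82% with none.

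**4. How often the arm comparison would find a 0.3 SD drop.** Assumptions: top versus $0, 192 per arm, log odds ratio −1 per SD, two-sided 0.05.
- All scored patients: SE = √(2/192) = 0.102; 0.3/0.102 = 2.94; power = Φ(2.94 − 1.96) = 84%. Simulation also gives 84%.
- Consenters, offer acts only through perceived risk: 51%.
- Consenters, offer also raises enrolment by a log odds of 0.5: 28%.
- Consenters, offer also raises enrolment by a log odds of 1.0: 15%.

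Sample size explains most of the first loss. With 96 per arm, SE = √(2/96) = 0.144 and power = Φ(2.08 − 1.96) = 55%. It does not explain the rest: the top arm has more consenters in the last two cases, yet detection falls. That is selection.

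**The case against.** Several counter-arguments stand in part.

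- **The operational rule is the interaction.** III.11.c says so, and overlooking risk is a slope effect for which perceived risk under the offer is the relevant score. If the top offer cuts the weight given to risk by 70%, the planned test gives an odds ratio of 2.04 and declares absence in only 5% of trials. The test is sound for that narrower claim.
- **The plan is not blind to lowered perception.** A consenters-only trend test found a 0.5 SD drop in 93–95% of simulated trials when the offer acted only through perceived risk. Smaller drops fare worse, as shown, and a null difference test does not exclude anything. The weighted analysis helps only as far as its consent model captures the selection. The SAP does not name that model's covariates.
- **The SAP expects the opposite direction.** This is true and should be stated beside the point. A hypothesis that risk perception will rise is not evidence that it did not fall.
- **The scores are not normal.** The SAP change table reports more than 85% of MOVE IT scores at 0 and extreme right skew in the smoking trial. The percentages above are therefore illustrations, and a floor limits how much lowering can register.

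A reader might infer that scoring risk after the offer makes the interaction null by construction, and that a pre-offer score should replace it. The documents do not support this. The planned score detects down-weighting, as the first item shows, and under a uniform drop both scores give the same answer (step 2). Otherwise each has a blind spot. If the offer compresses perceived risk by 70%, the pre-offer score gives 2.04 and absence in 5% of trials; the post-offer score gives 1.01 and 36%. If the offer doubles the spread and halves the weight, the pre-offer score gives 1.00 and 81%; the planned score gives 1.65 and 24%. A swap is a trade-off, not a correction.

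**Conclusion.** The point holds as a limit on what the plan can conclude. A similar slope across arms rules out a large change in risk sensitivity. It does not rule out a lowered level of perceived risk. That result needs only a common logistic slope and does not depend on the assumed effect sizes. Restricting the arm comparison to consenters weakens the one analysis that could fill the gap: an illustrative 0.3 SD drop is found in 15–51% of trials instead of about 84%, depending on how strongly the offer itself raises enrolment. Those percentages rest on normal scores, a log odds ratio of −1 per SD and 192 scored patients per arm.

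The restriction is also unnecessary for this outcome. The change table justifies it by the few non-consenters who would complete post-consent instruments, but the risk scale is given before the consent decision. The SAP 5.c model already needs scores from people who did not enrol.

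**What to change.** Change SAP 6.b and 6.c for perceived risk only:

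- Compare the earliest post-offer Compared Riskiness score by arm in all randomised patients with a score: the phone score in BASC, and the baseline-survey score in MOVE IT where collected.
- Use methods suited to a floor: the 0 versus >0 split already in SAP 6, alongside the Jonckheere-Terpstra test already in 6.c. Give confidence intervals, and state before the comparison is run how large a drop would matter.
- Report this beside the interaction. State that undue inducement is excluded only if both support it; otherwise limit the conclusion to no large change in risk sensitivity.
- Report the number scored by arm and the non-response among early decliners.

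Keep the post-offer score as the SAP 5.c moderator.

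The cost is one more analysis of data already planned, and a more guarded conclusion. No script or instrument changes. Two limits remain. Non-response may itself differ by arm, and a comparison of level would miss perceived risk being compressed around an unchanged mean, so the score distributions should be shown by arm.
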